2.1 Risk / Benefit Assessment

Efficacy of the mRNA-1273 vaccine was demonstrated in a phase 3 randomized trial of 30,420 participants in the COVD Study (3, 4). Vaccine efficacy in was 94.1% at preventing COVID-19 illness, including severe disease. Local and systemic reactions to the vaccine were common and included pain at injection site, headache, fatigue, myalgias and arthralgias. However, these reactions were transitory and there were no serious adverse events, episodes of thrombosis or myocarditis associated with the vaccine (3, 4). Hypersensitivity reactions were reported in 1.5% and 1.1% of participants in the vaccine and placebo groups, respectively.

Rare episodes of myocarditis and pericarditis have been reported after the mRNA vaccines (Pfizer-BioNTech and Moderna), particularly among young males after the second dose (9, 24, 25). The incidence of myocarditis/pericarditis is low and estimated at 3.5 cases per million doses after second dose mRNA among all adults, and 24.3 cases per million among individuals 12 to 29 years of age (10) . Most

reported cases of myocarditis/pericarditis occurred within the first 7 days of vaccination (7–9). Despite the potential for these rare but serious conditions, the benefit-risk assessment for Covid-19 vaccination remains strongly in favor of vaccination for those over age 5. Of note, myocarditis has also been associated with COVID-19 infection at a higher incidence than with the mRNA vaccines (6, 26). Analysis of a large national database found the risk ratio of myocarditis after vaccination to be 3.2 (95% CI 1.6-12.4) compared with those who were unvaccinated (6). After COVID-19 infection, the risk ratio of myocarditis was 18.3 (95% CI 4.0-25.1) compared with those who were unvaccinated.

The phase 1 mRNA-1273 clinical trial evaluated three doses: 25 ug, 100 ug and 250 ug. There was a dose-response relationship between increasing mRNA-1273 doses and serum anti-S-2P antibody levels. Systemic adverse reactions including fatigue, chills, headache, myalgia and injection site pain occurred in more than half the participants, and occurred more frequently with the 250 ug dose. Thus, the 100 ug dose was eventually chosen for the phase 3 clinical trial.

Lung transplant recipients, due to their immune suppression medicines, have had weak responses to the COVID-19 vaccines with antibody responses noted in less than 20% after the second vaccine dose (16–18). Lung transplantation is also unique among the solid organ transplants in the direct infection and injury of the allograft by SARS-CoV-2. Thus, lung transplant recipients have poor outcomes following COVID-19 infection with a high mortality rate. Third dose vaccines appear to improve immune responses for solid organ recipients, but has not been studied specifically for lung transplant recipients.

The current CDC guidance is for moderately or severely immunocompromised patients to receive a 50 ug booster: 1) At least 3 months after 3rd dose (first booster), and 2) At least 4 months after 4th dose (2nd booster). We believe that this dosing will be insufficient for many lung transplant recipients, particularly in those who did not receive any vaccine doses prior to their lung transplant, and leave them at high risk of poor COVID-19 outcomes. Importantly, due to their immunosuppression, lung recipients appear to have decreased side effects and reactogenicity to the SARS-CoV-2 vaccine.

We hypothesize that a 100 ug mid-dose and 200 ug high-dose mRNA-1273 booster dose can be safely administered to lung transplant recipients who previously received all of their vaccine doses after their lung transplant. We further hypothesize that the higher dose boosters will induce a stronger immune response to SARS-CoV-2 as measured by humoral and cellular response assays. The objectives of this study are to test these two hypotheses.

3 STUDY OBJECTIVES

3.1 Primary Objective

1. Evaluate safety of high-dose mRNA-1273 booster vaccine among lung transplant recipients measured by incidence of adverse events.
2. Evaluate reactogenicity of high-dose mRNA-1273 booster vaccine among lung transplant recipients measured by the FDA Toxicity Grading scale.

3.2 Secondary Objectives

1. Evaluate humoral immunogenicity measured by anti-RBD and anti-spike (S-2P) IgG levels at Day 30.

2. Evaluate humoral immunogenicity measured by neutralizing antibody titers from a pseudovirus neutralization assay at Day 30.
3. Evaluate cellular immunogenicity measured by cellular response assays including flow cytometry with intracellular staining at Day 30.

4 STUDY DESIGN

4.1 Study Overview

This is a Phase I/II open-label dose-finding trial among lung transplant recipients who received three or four mRNA vaccine doses (mRNA-1273 or BNT162b2) after lung transplantation to: standard-dose (50 ug), mid-dose (100 ug) or high-dose (200 ug) mRNA-1273 booster vaccine. Participants will be enrolled into three dose groups: 1) Standard-dose (50 ug) – 20 participants, 2) Mid-dose (100 ug) – 20 participants, 3) High-dose (200 ug) – 20 participants. The first 2 participants in both the mid-dose and high dose groups will be considered the ‘sentinel’ group. Participants in the sentinel group will receive the vaccine and undergo a 7-day observation period for safety and reactogenicity before additional participants are enrolled into that dose group.

Overall study enrollment will begin with the mid-dose sentinel group (n=2). During the observation period for the mid-dose sentinel group, we will enroll two participants into the standard-dose group. Once the mid-dose sentinel group completes their 7-day observation period without triggering halting rules and is approved to proceed by the DSMB, we will enroll the next 27 participants (Cohort 1) with a 2:1 randomization into the mid-dose (n=18) and standard-dose (n=9) groups.

Once all 20 participants have received their mid-dose vaccine without triggering halting rules and is approved to proceed by the DSMB, we will enroll the high-dose sentinel group (n=2). Once the high-dose sentinel group completes their 7-day observation period without triggering halting rules and is approved to proceed by the DSMB, we will enroll the next 27 participants (Cohort 2) with a 2:1 randomization into the high-dose (n=18) and standard-dose (n=9) groups. Thus, all 20 participants in the mid-dose group will be enrolled prior to enrollment of the high-dose group.

We will perform stratified randomization for the two cohorts based on: 1) the number of prior doses, and 2) prior receipt of any BNT162b2 vaccines. Randomization will be done by the UCLA Clinical and Translational Science Institute (CTSI) statistics team based on scheduled participants prior to the study visit. The 6 participants in the sentinel (n=4) and initial (n=2) groups (Table 1) will be assigned into the 3 groups based on their scheduled visit day.

This clinical trial is designed to assess the safety, reactogenicity and immunogenicity of mid and high-dose mRNA-1273 vaccine among lung transplant recipients who have received three or four prior mRNA vaccines.

[figure not shown]
In-person visits will occur on Days 1 (booster vaccine), 7 and 30. Telephone visits will occur on Days 3, 90 and 180. Adverse events will be assessed in person (Days 1, 7 and 30) and by telephone calls (Days 3, 90 and 180). All follow-up visits will include a detailed review for serious adverse experiences (SAEs), adverse events of special interest (AESIs) and medically attended adverse events (MAAEs).

Table 1: Treatment Arms:

Groups will be enrolled as follows:	n	Dose
1) Mid-dose – Sentinel group	2	100 ug
2) Standard-dose – Initial group	2	50 ug
3) Cohort 1: 2:1 Randomization into		
Mid-dose group	18	100 ug
Standard-dose group	9	50 ug
4) High-dose – Sentinel group	2	200 ug
5) Cohort 2: 2:1 Randomization into		
High-dose group	18	200 ug
Standard-dose group	9	50 ug

Cohorts 1 and 2 will be randomized to their dose and considered the full group.

Figure 1. Study enrollment flow diagram

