8 STUDY TREATMENTS

8.1 Method of Assigning Participants to Treatment Groups

This is a Phase I/II open-label dose-finding trial among lung transplant recipients who received three or four mRNA vaccine doses (mRNA-1273 or BNT162b2) after lung transplantation to: standard-dose (50 ug), mid-dose (100 ug) or high-dose (200 ug) mRNA-1273 booster vaccine. Participants will be enrolled into three dose groups: 1) Standard-dose – 20 participants, 2) Mid-dose – 20 participants, 3) High-dose – 20 participants. The first 2 participants in both the mid-dose and high dose groups will be considered the ‘sentinel’ group. Participants in the sentinel group will receive the vaccine and undergo a 7-day observation period for safety and reactogenicity before additional participants are enrolled into that dose group.

Overall study enrollment will begin with the mid-dose sentinel group (n=2). During the observation period for the mid-dose sentinel group, we will enroll two participants into the standard-dose group. Once the mid-dose sentinel group completes their 7-day observation period without triggering halting rules and is approved to proceed by the DSMB, we will enroll the next 27 participants (Cohort 1) with a 2:1 randomization into the mid-dose (n=18) and standard-dose (n=9) groups.

Once all 20 participants have received their mid-dose vaccine without triggering halting rules and is approved to proceed by the DSMB, we will enroll the high-dose sentinel group (n=2). Once the high-dose sentinel group completes their 7-day observation period without triggering halting rules and is approved to proceed by the DSMB, we will enroll the next 27 participants (Cohort 2) with a 2:1 randomization into the high-dose (n=18) and standard-dose (n=9) groups. All 20 participants in the mid-dose group will be enrolled prior to enrollment of the high-dose group.

We will perform stratified randomization for the two cohorts based on: 1) the number of prior doses, and 2) prior receipt of any BNT162b2 vaccines. Randomization will be done by the UCLA Clinical and Translational Science Institute (CTSI) statistics team based on scheduled participants prior to the study visit. The 6 participants in the sentinel (n=4) and initial (n=2) groups (Table 1) will be assigned into the 3 groups based on their scheduled visit day.

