14 STATISTICAL METHODS AND CONSIDERATIONS

14.1 General Considerations

Data collected in this study will be presented using summary tables and participant data listings. Continuous variables will be summarized using descriptive statistics, specifically the mean, median, standard deviation, minimum, and maximum. Categorical variables will be summarized by frequencies and percentages. Data Sets Analyzed:

- **Intent-to-Treat (ITT) Analysis Set**

The ITT analysis set includes all participants who are enrolled into a treatment (dose) group regardless of whether participants receive any study drug(s), or receive a different regimen from the regimen they were randomized to. Participants will be assigned into a dose group as described above.

- **Safety Analysis Set**

A safety analysis set will include data from participants who receive at least one dose of study treatment, with treatment assignments designated according to the actual treatment received. This analysis set will be used in the analyses of safety variables (primary endpoint) as well as study treatment administration.

- **Per-Protocol (PP) Analysis Set**

The PP analysis set includes data from participants in the ITT analysis set who meet the general criteria defining the target population for this study, are adherent to the protocol, are compliant with study drug treatment, and are evaluable for relevant efficacy endpoints. Treatment assignment will be designated according to the actual treatment received. The PP analysis set will be used in the analyses of the secondary endpoints. The PP analysis set will only include participants randomized to the dose-group (Cohorts 1 and 2, Figure 1). The PP analysis set will exclude participants in the sentinel mid-dose (n=2), sentinel high-dose (n=2) and initial standard-dose groups (n=2) who were not randomized to their dose-group. Participants who are found to have detectable anti-N-protein IgG antibody levels (representing prior infection) at their Day 1 (baseline) visit will be excluded from the PP analysis set.

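### Moving the two non-randomised "initial" standard-dose places into the randomised cohorts would raise the planned maximum of standard-dose participants in the immunogenicity analyses from 18 to 20, with no extra enrolment

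*Combined protocol and SAP*

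**What the plan says.** Enrolment opens with two mid-dose sentinels. While they are observed, section 4.1 fills two standard-dose places: "During the observation period for the mid-dose sentinel group, we will enroll two participants into the standard-dose group". Table 1 lists these as the standard-dose initial group. Section 8.1 says that the four sentinels and these two "will be assigned into the 3 groups based on their scheduled visit day".

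The randomised part follows in two steps. In Cohort 1, "we will enroll the next 27 participants (Cohort 1) with a 2:1 randomization into the mid-dose (n=18) and standard-dose (n=9) groups". In Cohort 2, "we will enroll the next 27 participants (Cohort 2) with a 2:1 randomization into the high-dose (n=18) and standard-dose (n=9) groups".

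Section 14.1 fixes the analysis set for immunogenicity: "The PP analysis set will be used in the analyses of the secondary endpoints". It limits that set to Cohorts 1 and 2 and names the omissions: "The PP analysis set will exclude participants in the sentinel mid-dose (n=2), sentinel high-dose (n=2) and initial standard-dose groups (n=2) who were not randomized".

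The Safety Analysis Set in 14.1 includes everyone who is dosed, by treatment received, and is used for the primary endpoint. The two also fit the ITT definition, but no analysis is assigned to the ITT set. The optional interim in 14.7 covers the same secondary endpoints and names no set.

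**The concern.** Sentinels have to be assigned without randomisation, because their purpose is to let a higher dose be observed before others receive it. That reason does not extend to 50 ug. Section 2 describes 50 ug as the currently recommended booster, and neither 4.1 nor 12.2 gives it a sentinel stage. The sample-size text in 14.6 explains the sentinels but says nothing about the initial pair.

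Given assignment by visit day, leaving the two out of the PP set is correct. The avoidable step is the assignment itself. Section 10 has every participant give blood for antibody and cellular assays on Days 1, 7 and 30, so these two supply samples that enter no planned immunogenicity comparison. Standard dose is the comparator in every planned contrast, so each control lost costs precision in both the high-dose and the mid-dose comparison.

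**Working it through.** **Inputs.** From 14.6: expected mean log10 IgG increase 0.23 (50 ug) and 0.91 (200 ug), SD 0.63, two-sided alpha 0.05, target power 80%, minimum 15 per group. From 4.1 and Table 1: 9 standard-dose and 18 higher-dose participants in each randomised cohort, with 2 standard-dose and 4 sentinel participants outside the randomisation.

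**Formula.** Exact power of the two-sample t-test from the noncentral t distribution, with df = n1 + n2 − 2 and noncentrality = difference / [SD × √(1/n1 + 1/n2)]. The difference is 0.91 − 0.23 = 0.68.

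**The plan's figure.** 14 per group gives 78.5% and 15 per group gives 81.4%. The stated minimum of 15 is reproduced.

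**Counts.**
- Now: standard-dose participants eligible for the PP set = 9 + 9 = 18. Randomised in total: 27 + 27 = 54, with 6 outside.
- After the change: 10 + 10 = 20, or 9 + 11 = 20. Randomised in total: 28 + 28 = 56, or 27 + 29 = 56, with 4 sentinels outside. Either way the total is 60, with 20 per dose.

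**Planned contrast, high dose versus all randomised standard-dose participants.**

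| High v standard | 1/n1 + 1/n2 | SE | Noncentrality | Power |
|---|---|---|---|---|
| 18 v 18 (now) | 0.1111 | 0.210 | 0.68/0.210 = 3.24 | 88.2% |
| 18 v 20 (changed) | 0.1056 | 0.205 | 0.68/0.2047 = 3.32 | 89.8% |

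The gain is 1.6 percentage points. The variance factor falls by (0.1111 − 0.1056)/0.1111, about 5%. The difference detectable with 80% power falls from 0.606 to 0.589 log10.

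**Mid dose versus standard dose.** The expected difference is 0.46 − 0.23 = 0.23. Power goes from 18.7% to 19.4%, which is low either way.

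**Further PP losses.** Section 14.1 also removes participants with detectable anti-N antibody at baseline and those who are non-adherent or not evaluable. It states no rate. Assuming equal proportional loss in both groups, high- versus standard-dose power moves from 84.5% to 86.4% at 10% loss, and from 79.7% to 81.9% at 20% loss.

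**Concurrent controls only (not a planned analysis).** If 200 ug were compared only with the standard-dose participants in Cohort 2:

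| High v standard | 1/n1 + 1/n2 | Power |
|---|---|---|
| 18 v 9 (now) | 0.1667 | 71.9% |
| 18 v 10 | 0.1556 | 75.0% |
| 18 v 11 | 0.1465 | 77.6% |

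**The case against.** The strongest reply is that nothing here is wrong. The allocation text, Table 1 and 14.1 agree with each other, and the PP set properly keeps out people who were not randomised. The sponsor may want to keep enrolling while mid-dose is on hold. All of that stands: this is a choice that could be made better, not a contradiction or a source of bias.

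A reader might infer that the two participants are wasted. The documents do not support that. The primary objectives are safety and reactogenicity, and both participants count fully in the standard-dose safety tables.

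A reader might also take the movement from about 72% to 75% or 78% as the size of the benefit. Section 14.4 compares the standard-dose group with the high-dose group and does not restrict controls to Cohort 2, so those figures belong to an analysis that the plan does not specify. Even 18 v 11 stays below 80%. On the planned contrast the gain is 1.6 points, and 18 per group already exceeds the stated minimum of 15.

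Finally, the two cannot simply be randomised where they now stand, because mid-dose enrolment is on hold that week. The places have to move to a later cohort. Adding two people at 2:1 would not produce two more controls, so the counts have to be fixed. These points shape the change but do not defeat it.

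**Conclusion.** The point holds as a minor, inexpensive improvement. Two of 20 standard-dose participants (10%) are kept out of every planned immunogenicity comparison by an assignment rule for which no reason is given. Moving their places into the randomisation raises the planned maximum of controls from 18 to 20 and power for the pooled high- versus standard-dose contrast from 88.2% to 89.8%.

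This rests on the plan's own difference and SD, and on pooling standard-dose participants across both cohorts, as 14.4 reads. Both 18 and 20 are ceilings before other PP exclusions, whose rates are not stated. It does not show that the study is underpowered for its high-dose contrast, and it has no bearing on the primary safety analysis.

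**What to change.** Drop the non-randomised initial group and put its two standard-dose places in the randomised cohorts with fixed counts. One option is 18:10 in each cohort, which spreads the gain over both periods. The other is 18:11 in Cohort 2, which puts both extra controls alongside the high-dose group. The PP set then excludes by name only the four sentinels.

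Text to change:
- the synopsis, 4.1, Table 1, 8.1 and 14.1;
- the standard-dose n=18 in 12.3, which becomes 20;
- the counts behind the 1:2 fallback in 8.1, 12.3 and 14.6.

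The fallback needs restating because its arithmetic now fits exactly. If the high-dose group stops after its sentinels, 60 − 33 = 27 places remain, and 9 mid-dose and 18 standard-dose bring each group to 29. After the change, 28 or 29 places remain and neither divides 1:2. Fixed counts of 9 and 19 (18:10 option) or 9 and 20 (18:11 option) would still give 29 in each group.

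Costs: a protocol amendment, no standard-dose enrolment during the first sentinel week, a ratio slightly off 2:1, and a new stratified randomisation list. A 2:1 ratio can use blocks of three, whereas 18:10 reduces only to 9:5 (blocks of 14) and 18:11 does not reduce, so the list must be built to fixed totals. If the initial group serves an operational purpose, stating it in 4.1 is the alternative.
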